11. PLANS FOR DISSEMINATING AND COMMUNICATING STUDY RESULTS

11.1. Target Audience

The information generated by this study will be transmitted to Regulatory Authorities, primarily the EMA, as required, and will contribute to the published literature. The results may be disseminated externally via manuscripts or presentations.

11.2. Study reporting and publications

Whenever 10 parents/carers and 10 HCPs have completed the surveys, a final report will be submitted to the EMA within six months of the end of data collection. See Section 7 for milestones related to this study, which are contingent upon uptake of Strimvelis.

The final report will encompass all planned analyses, including a description of the complete study population, as described above.

In accordance with the 2010 EU pharmacovigilance legislation, information about this Post-authorisation Safety Study will be entered into the publically available European Network of Centres for Pharmacoepidemiology and Pharmacovigilance (ENCePP) Register of Studies. The study protocol will be entered into the register before the start of data collection and will also be entered into clinicaltrials.gov. Updates to the study protocol in case of substantial amendments, progress reports where applicable, and the final study report will also be entered in the register.

Any publication of the results from this study will be consistent with GSK's publication policy and guided by the Uniform Requirements for Manuscripts Submitted to Biomedical Journals: Writing and Editing for Biomedical Publication of the International Committee of Medical Journal Editors (ICMJE), updated April 2010 (ICMJE, 2010). To comply with the requirements of the EU Pharmacovigilance Regulation, the final manuscript of the article will be submitted to the Agency and competent authorities, within two weeks of the first acceptance for publication.

13. ANNEX 1: LIST OF STAND-ALONE-DOCUMENTS

No.	Document	Date	Title
	Reference No		
1.		<date></date>	GSK Epidemiology and Health Outcome PVP approval form >
2.	<no></no>	<date></date>	<text></text>
N	<no></no>	<date></date>	<text></text>

14. ANNEX 2: LIST OF TABLE AND FIGURE SHELLS

14.1. Tables

Table 1. Survey participant summary

	HCP survey	Parent/Carer survey	
Number of participants screened			
Number of participants terminated			
Number of participants completed the survey			
Total			

 Table 2: HCP survey - availability and review of Educational Materials

	Yes (N, %)	No (N, %)	Total (N, 100%)	
 Have you received copies of the following Educational Materials on Strimvelis for healthcare practitioners? Important risk minimization information for healthcare professionals who provide long- term follow-up of ADA-SCID patients post- treatment with Stimvelis. Summary of Product Characteristics (SmPC). 				
If you answered "No" to all of the above materials, prior to this survey, were you aware of these educational materials about Strimvelis?				
	Yes	No	Some	N total (% Yes)
Did you read the provided Educational Materials about Strimvelis?				
 If Some, which ones did you read? Important risk minimization information for healthcare professionals who provide long-term follow-up of ADA-SCID patients post-treatment with Strimvelis. Summary of Product Characteristics (SPC). 				

Table 3. Listing of HCP Survey Responses for each survey question

Survey Question	Answer	N	% (total)
Demography Q1. How			
many patients have you			
referred to for treatment			

Survey Question	Answer	N	% (total)
with Strimvelis?			
Demography Q2. How would you classify your	a. Paediatrician		
<pre>primary medical speciality?</pre>	b. Immunologist		
	c. Haematologist		
	d. Other (please specify):		
Demography Q3. In what country is your primary medical practice?			
Demography Q4. What is the length of your	a. Less than 3 years		
experience in your primary medical speciality?	b. More than 3 and up to 5 years		
	c. More than 5 and up to 10 years		
	d. More than 10 and up to 15 years		
	e. More than 15 years		
	f. Prefer not to answer		
Demography Q5. How many patients with ADA-SCID are you currently treating?			
1. Have you received copies of the following educational materials about Strimvelis for healthcare providers?	a. Important risk minimization information for healthcare professionals who provide long-term follow-up of ADA-SCID patients post-treatment with Strimvelis.		
	b. Summary of Product Characteristics (SPC).		

Survey Question	Answer	N	% (total)
If you answered "No" to all of the above	a. Yes		
materials, prior to this survey, were you aware	b. No		
of these educational materials about Strimvelis?	c. I don't know (I cannot remember)		
2. Did you read the provided educational	a. Yes		
materials about Strimvelis?	b. No		
	c. Some		
	d. I don't know		
3. Strimvelis is recommended as first-	a. True		
line therapy for any patient affected by	b. False		
ADA-SCID.	c. I don't know		
4. Strimvelis is indicated for the	a. True		
treatment of patients with severe combined	b. False		
immunodeficiency due to ADA deficiency, for whom no suitable HLA matched related stem cell donor is available.	c. I don't know		
5. Strimvelis is contraindicated in patients with a history	a. True		
of previous gene therapy.	b. False		
	c. I don't know		
6. Patients eligible to receive treatment with	a. True		
Strimvelis should have a bone marrow harvest for stem cell back-up at	b. False		
least 3 weeks prior to treatment with Strimvelis.	c. I don't know		

Survey Question	Answer	N	% (total)
7. Parents and carers of patients receiving	a. True		
treatment with Strimvelis should be educated on the fact that the patient should not be able to donate blood, organs, tissues, or cells for transplantation.	b. False		
	c. I don't know		
8. It is recommended that patients treated	a. True		
with Strimvelis are regularly followed up	b. False		
clinically (at least annually).	c. I don't know		
KRM 1: Gene therapy f	or ADA-SCID and malig	gnancy risk (e.g. leukae	mia)
9. Strimvelis is contraindicated in	a. True		
patients with a current or previous history of	b. False		
leukaemia or myelodysplasia.	c. I don't know		
10. Have you given advice to parents/carers/patients regarding monitoring for signs and symptoms	a. Yes		
	b. No		
of leukaemia?	c. I don't know		
11. Have you performed blood tests	a. Yes		
(including red blood cell indices, white	b. No		
blood cell count differential, platelet	c. I don't know		
count, and a routine biochemistry screen)			
within the first year of a patient's returning from treatment with Strimvelis?			

Survey Question	Answer	N	% (total)	
KRM 2: Autoimmunity				
12. Regular monitoring for clinical autoimmunity (possibly	a. True b. False			
including tests for auto- antibodies) is recommended.	c. I don't know			
13. Autoimmunity may be observed during	a. True			
immune reconstitution after gene therapy.	b. False			
	c. I don't know			
KRM 3: Unsuccessful re	esponse to gene therapy			
14. Strimvelis is not proven, nor likely to be	a. True			
effective for the non- immunological aspects	b. False			
of the disease (e.g. hepatic steatosis, CNS manifestations, and hearing and neurobehavioural disorders).	c. I don't know			
15. Patients should be followed up indefinitely	a. True			
using routine haematological tests.	b. False			
	c. I don't know			
16. Which tests can be used during follow-up if loss of immunity is suspected?	a. Lymphocyte counts, including T-cell differential counts.			
	b. T-cell function [as measured by T-cell proliferative capacity to mitogen challenge (TCA/PHA)].			
	c. ADA metabolite levels (e.g. dAXP levels).			

Answer	N	% (total)
a. Yes b. No c. I don't know		
a. Yes b. No c. I don't know		
a. Trueb. Falsec. I don't know		
a. True b. False c. I don't know		
	a. Yes b. No c. I don't know a. Yes b. No c. I don't know a. True b. False c. I don't know a. True b. False	a. Yes b. No c. I don't know a. Yes b. No c. I don't know a. True b. False c. I don't know a. True b. False

 Table 4. Summary of HCP survey results

		Correct answer		
No.	Question	Yes	No	N total; %Yes
1	Have you received copies of the following educational materials about Strimvelis for healthcare providers?			
2	Did you read the provided educational materials about Strimvelis?			

		Correct answer		
No.	Question	Yes	No	N total; %Yes
3	Strimvelis is recommended as			, , , , , , , , , , , , , , , , , , , ,
	first-line therapy for any			
	patient affected by ADA-			
	SCID.			
4	Strimvelis is indicated for the			
	treatment of patients with			
	severe combined			
	immunodeficiency due to			
	ADA deficiency, for whom no			
	suitable HLA matched related			
	stem cell donor is available.			
5	Strimvelis is contraindicated in			
	patients with a history of			
	previous gene therapy.			
	provious gene merupy.			
	Total (Q1-5)			
Gene	therapy for ADA-SCID and malign	nancy risk (e.g. leuk	kaemia)	
6	Patients eligible to receive			
	treatment with Strimvelis			
	should have a bone marrow			
	harvest for stem cell back-up at			
	least 3 weeks prior to treatment			
	with Strimvelis.			
7	Parents and carers of patients			
	receiving treatment with Strimvelis should be educated			
	on the fact that the patient			
	should not be able to donate			
	blood, organs, tissues, or cells			
	for transplantation.			
8	It is recommended that patients			
	treated with Strimvelis are			
	regularly followed up			
	clinically (at least annually).			
9	Strimvelis is contraindicated in			
	patients with a current or			
	previous history of leukaemia			
	or myelodysplasia.			
10	Have you given advice to			
	parents/carers/patients			
	regarding monitoring for signs			
11	and symptoms of leukaemia?			
11	Have you performed blood			
	tests (including red blood cell			
	indices, white blood cell count differential, platelet count, and			
	a routine biochemistry screen)			
	within the first year of a			
	patient's returning from			
L	Parioni o retaining moni	I	1	

			Correct answer	
No.	Question	Yes	No	N total; %Yes
110.	treatment with Strimvelis?	100	110	11 total, 701 cs
	Total (Q6-11)			
Autoir	mmunity			
12	Regular monitoring for clinical			
12	autoimmunity (possibly			
	including tests for auto-			
	antibodies) is recommended.			
13	Autoimmunity may be			
13	observed during immune			
	reconstitution after gene			
	therapy.			
	Total (Q12,13)			
Unsuc	ecessful response to gene therapy			
14	Strimvelis is not proven, nor			
1	likely to be effective for the			
	non-immunological aspects of			
	the disease (e.g. hepatic			
	steatosis, CNS manifestations,			
	and hearing and			
	neurobehavioural disorders).			
15	Patients should be followed up			
10	indefinitely using routine			
	haematological tests.			
16	Which tests can be used during			
	follow-up if loss of immunity			
	is suspected?			
17	In patients treated with			
	Strimvelis, elevated red blood			
	cell dAxP levels may indicate			
	loss of ADA enzyme activity			
	and failure of gene therapy.			
18	In patients treated with			
	Strimvelis, if you suspect a			
	loss of efficacy or inadequate			
	efficacy for the immunological			
	manifestations of ADA-SCID,			
	can patients still be considered			
	for treatment with enzyme			
	replacement therapy (ERT) or			
	subsequent bone marrrow			
	transplant (BMT)?			
	Total (Q14-18)			
Pregna				
19	Strimvelis is intended to			
	correct the ADA gene defect in			
	patient gametes (e.g. ovum,			
2.2	sperm).			
20	Family planning advice should			
	be given to patients when it is			

		Correct answer		
No.	Question	Yes	No	N total; %Yes
	appropriate for their ages and			
	circumstances.			
	Total (Q19,20)			
	Total (Q1-20)			

 Table 5. HCP demographics

Survey Question	Answer	N	%
Demography Q1. How many patients have you referred to for treatment with Strimvelis?			
Demography Q2. How would you classify your primary	a. Paediatrician b. Immunologist		
medical speciality?	c. Haematologist		
	d. Other (please specify):		
Demography Q3. In what country is your primary medical practice?		<listing></listing>	

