8.2. Study Population and Setting

Strimvelis is indicated for the treatment of patients with ADA-SCID, for whom no suitable human leukocyte antigen (HLA)-matched related stem cell donor is available. A registry study (PRJ2684/200195) will be implemented with long-term prospective, non-interventional follow-up of the safety and effectiveness of Strimvelis. Patients in the registry will be monitored for at least 15 years post-treatment with Strimvelis.

Parents/carers and referring HCPs of patients enrolled within this registry will be contacted separately and asked to participate in their respective surveys evaluating the effectiveness of risk minimisation measures. The survey will be conducted via telephone interviews in the local languages for parents/carers and for referring HCPs. Parent/Carers and referring HCPs survey are distinct and results will not be linked for confidentiality reasons.

In order to be considered eligible to participate in the study, HCPs will be required to meet the following criteria:

- HCPs or HCPs' close family members may not have been employees of GlaxoSmithKline, Pharmaceutical Product Development, LLC (PPD), the Food and Drug Administration (FDA), or the European Medicines Agency (EMA).
- HCPs must be licensed.
- An HCP must not have previously completed a survey regarding Strimvelis educational materials.
- An HCP must have previously referred a patient for Strimvelis treatment.

In order to be considered eligible to participate in the Parent/Carer survey, parents or carers will be required to meet the following criteria:

 Parents/carers or parents'/carers' close family members may not have been employees of GlaxoSmithKline, Pharmaceutical Product Development, LLC (PPD), the Food and Drug Administration (FDA), or the European Medicines Agency (EMA).

- A parent/carer must not have previously completed a survey regarding Strimvelis educational materials
- A parent's or carer's child must have previously received treatment with Strimvelis.

The study will recruit for approximately two years until 10 referring HCPs and 10 parents/carers have completed their respective surveys (length of study may vary contingent upon product uptake).

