8.3.3. Outcome definitions

This study will assess the proportion of parents/carers and referring HCPs at six months post treatment with Strimvelis that understood the possible risks relating to:

Safety concerns (KRM topics):

- 1. Malignancy due to insertional oncogenesis (e.g. leukaemia, myelodysplasia)
- 2. Autoimmunity
- 3. Unsuccessful response to gene therapy
- 4. Pregnancy

Other areas of interest:

- Requirement for long-term monitoring
- Receipt of the patient treatment alert card

The proportion of parents/carers and referring HCPs who acknowledge receipt of routine and additional risk minimization measures (e.g., SmPC/PIL, educational materials, Patient Alert Card) will be assessed as a measure of implementation.

The type of medical specialty and experience of referring HCPs will be summarized.

The primary outcome of these surveys is the proportion of parents/caregivers and referring HCPs that provide correct responses to a series of questions concerning the specific risks associated with Strimvelis.

Sufficient understanding of a key risk message can be assumed if at least 80% or more respondents correctly answer all questions that are included within that particular key risk message [ISPE White Paper 2016].

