8.5. Study size

All parents/carers and referring HCPs from patients enrolled in the Strimvelis product registry will be invited to complete the surveys. The study will recruit for approximately two years until 10 referring HCPs and 10 parents/carers have completed their respective surveys (length of study may vary contingent upon product uptake).

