Please answer based on your knowledge of Strimvelis as informed by the Strimvelis Educational Materials, including the product Summary of Product Characteristics (Product Label).
3. Strimvelis is recommended as first-line therapy for any patient affected by ADA-SCID.
Please select one response.
a. True
b. False
c. I don't know
4. Strimvelis is indicated for the treatment of patients with severe combined immunodeficiency due to ADA deficiency, for whom no suitable HLA matched related stem cell donor is available.
Please select one response.
a. True
b. False
c. I don't know
5. Strimvelis is contraindicated in patients with a history of previous gene therapy.
Please select one response.
a. True
b. False

c. I don't know

CONFIDENTIAL

WWEpi Project number: PRJ2678/205881

6. Patients eligible to receive treatment with Strimvelis should have a bone marrow harvest for stem cell back-up at least 3 weeks prior to treatment with Strimvelis. Please select one response. a. True b. False c. I don't know 7. Parents and carers of patients receiving treatment with Strimvelis should be educated on the fact that the patient should not be able to donate blood, organs, tissues, or cells for transplantation. Please select one response. a. True b. False c. I don't know 8. It is recommended that patients treated with Strimvelis are regularly followed up clinically (at least annually). Please select one response. a. True b. False c. I don't know 9. Strimvelis is contraindicated in patients with a current or previous history of leukaemia or myelodysplasia. [KRM 1] Please select one response. a. True b. False

c. I don't know

CONFIDENTIAL

WWEpi Project number: PRJ2678/205881

10. Have you given advice to parents/carers/patients regarding monitoring for signs and symptoms of leukaemia? [KRM1] Please select one response. a. Yes b. No c. I don't know 11. Have you performed blood tests (including red blood cell indices, white blood cell count differential, platelet count, and a routine biochemistry screen) within the first year of a patient's returning from treatment with Strimvelis? [KRM1] Please select one response. a. Yes b. No c. I don't know 12. Regular monitoring for clinical autoimmunity (possibly including tests for auto-antibodies) is recommended. [KRM2] Please select one response. a. True b. False c. I don't know 13. Autoimmunity may be observed during immune reconstitution after gene therapy. [KRM2] Please select one response. a. True b. False

b. No

c. I don't know

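### Questions about past conduct are scored as understanding of the malignancy message (KRM1), so fully informed respondents can fail it; receipt and reading are also scored as correct answers

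*Protocol*

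**What the plan says.** Section 8.3.3 of the protocol defines the primary outcome as the proportion of each group "that provide correct responses to a series of questions concerning the specific risks associated with Strimvelis". It takes understanding of a key risk message as sufficient if "at least 80% or more respondents correctly answer all questions that are included within that particular key risk message". The same section says that acknowledged receipt of the materials "will be assessed as a measure of implementation", which sets receipt apart from understanding. Section 8.7.1 summarises every question as answered correctly or incorrectly, gives the proportion correct overall and by risk category, and refers to the Annex 2 table shells.

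In Annex 4 the HCP survey prints "10. Have you given advice to parents/carers/patients regarding monitoring for signs and symptoms of leukaemia? [KRM1" with the KRM1 tag at its end. Q11 carries the same tag and begins "Have you performed blood tests (including red blood cell indices, white blood cell count differential, platelet count, and a routine biochemistry screen". Both offer Yes, No or don't know. In Table 3 the KRM1 heading covers Q9-11. In Table 4 the malignancy block is Q6-11. For parents/carers, Tables 7 and 8 both place Q7 (whether the child was seen by the specialist in the last 6 months) in the malignancy block Q6-8.

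Table 4 also lists Q1, "Have you received copies of the following educational materials about Strimvelis for healthcare providers", and Q2 (whether they were read) under its correct-answer column. Both enter Total (Q1-5) and Total (Q1-20). Table 8 puts the parent versions of Q1 and Q2 into its own Total (Q1-5).

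On who is asked and when: section 8.2 states "An HCP must have previously referred a patient for Strimvelis treatment", section 8.1 places the survey about six months after treatment, and section 8.5 states "The study will recruit for approximately two years until 10 referring HCPs and 10 parents/carers have completed their respective surveys".

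**The concern.** The KRM criterion is meant to show understanding. HCP Q10 and Q11 and parent Q7 record events. A No describes what happened in that patient's care and need not be an error of knowledge. An HCP can qualify by having referred a patient without being the doctor who follows that patient afterwards. The interview also takes place partway through the one-year window of Q11, and section 8.6.3 provides for no later contact.

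Because a respondent must get every question in the KRM right, adding conduct items can only lower the KRM1 proportion. With 10 completers per survey, a few truthful No answers can turn the malignancy message from understood to not understood.

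Receipt and reading raise a smaller and separate problem. They are reported as correct or incorrect risk answers, and they can move the totals in either direction without any difference in knowledge.

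**Working it through.** The protocol gives no sample-size or precision figure for this criterion, so there is nothing to reproduce. The check has three parts.

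**1. Item counts (Annex 2 tables and Annex 4 tags)**

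| Score | Items | Conduct, receipt or reading items | Share |
|---|---|---|---|
| HCP KRM1, Table 3/Annex 4 | Q9-11 | Q10, Q11 | 2 of 3 |
| HCP malignancy block, Table 4 | Q6-11 | Q10, Q11 | 2 of 6 |
| Parent KRM1, Tables 7 and 8 | Q6-8 | Q7 | 1 of 3 |
| HCP overall, Table 4 | Q1-20 | Q1, Q2, Q10, Q11 | 4 of 20 |

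An HCP with every knowledge item right and a No to all four scores 16/20 = 80% overall, 3/5 on Q1-5 and 4/6 on Q6-11. A parent with every knowledge item right and a No to Q1, Q2 and Q7 has 13 of 16 = 81%. Table 8 shows no overall row, so a parent overall figure arises only from the general sentence in section 8.7.1.

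**2. The 80% rule with 10 completers**

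0.80 × 10 = 8, so at least 8 respondents must have all KRM1 items correct.

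- Two truthful No respondents: 8/10 = 80%. KRM1 is met, with no room for a single knowledge error.
- Three: 7/10 = 70%. KRM1 is not met, whatever anyone knows.

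**3. Chance of meeting 80% when all 10 are fully informed**

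The rate of truthful No answers is an assumption, since the protocol gives none. Let q be the probability that a respondent has no No on any conduct item. Then

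P(X ≥ 8) = 45q⁸(1−q)² + 10q⁹(1−q) + q¹⁰.

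Worked at q = 0.9: 0.1937 + 0.3874 + 0.3487 = 0.93.

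| Assumed rate of No | (a) rate applies to at least one conduct item: q, P | (b) rate applies to each of Q10 and Q11, independent: q, P |
|---|---|---|
| 5% | 0.95, 0.99 | 0.95² = 0.9025, 0.93 |
| 10% | 0.90, 0.93 | 0.90² = 0.81, 0.71 |
| 20% | 0.80, 0.68 | 0.80² = 0.64, 0.24 |
| 30% | 0.70, 0.38 | 0.70² = 0.49, 0.05 |

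Column (a) also covers parents, who have the single item Q7. With the conduct items unscored, a fully informed group meets the criterion with probability 1.

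**The case against.** There is a fair case that truthful No answers will be few. Section 8.3.1 names HCP material addressed to professionals who follow patients over the long term. Section 9.1 speaks of HCPs involved in the registry. Section 8.9 says the interview coincides with the registry's follow-up, which makes a visit in the last 6 months likely and weakens the point for parent Q7. If the rate is near 5%, the loss is small. All this bears on how often the problem bites. It does not make a conduct item a test of understanding, and the eligibility rule still asks only for a referral.

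An analysis plan foreseen in section 8.6.2 could rescore the items. The protocol itself, however, fixes the KRM tags and the correct-answer column. Tables 3 and 7 would show how many said No to each question, so the effect would be partly visible. They would not show which respondents had every knowledge item right.

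Three stronger readings are tempting and are not supported:

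- **That the one-year window makes Q11 unanswerable at six months.** An HCP who has already tested can truthfully say Yes. The timing makes a No possible and does not force it.
- **That receipt and reading can fail KRM1.** They lie outside every KRM, and no threshold attaches to Total (Q1-5) or Total (Q1-20). Total (Q1-20) is in Table 4 only.
- **That 0.38 is the expected chance of success.** It follows from one assumed rate within a range, and nothing in the protocol supports 30% over 5%.

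**Conclusion.** The point holds. HCP Q10 and Q11, and more weakly parent Q7, measure conduct but count toward a criterion for understanding. Three truthful No respondents among 10 are enough to fail KRM1 at 70% when everyone is fully informed. That result needs only 10 completers and the all-questions rule, with Yes taken as the correct answer; no other response to these items could plausibly be scored as correct. The probabilities (0.93, 0.68 and 0.38 at 10%, 20% and 30%; 0.71, 0.24 and 0.05 if Q10 and Q11 are independent at those rates) further assume perfect knowledge, independent respondents and the stated rates.

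The scoring of receipt and reading contradicts section 8.3.3, but it affects only totals without a decision rule. It is the lesser part of the point.

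**What to change.** 1. Remove Q1 and Q2 from the correct-answer columns and totals of Tables 4 and 8. Tables 2 and 6 already report receipt and reading.
2. Report HCP Q10 and Q11 and parent Q7 as unscored implementation or behaviour items. Their responses stay in Tables 3 and 7, and the Q7 sub-questions in Table 9.
3. State in sections 8.3.3 and 8.7.1 that KRM and overall scores use knowledge items only.
4. Change the KRM tags in Annex 4 and the groupings and total labels in Tables 3, 4, 7 and 8 to match.
5. Reconcile whether HCP Q6-8 belong to KRM1 (as in Table 4) or not (as in Table 3 and Annex 4).

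The cost is text and table edits. Every question is still asked and no extra respondents are needed. The drawback is a thinner KRM1: parents keep Q6 and Q8, while HCPs keep Q6-9, or Q9 alone if Q6-8 are excluded. Step 5 therefore has to be settled together with step 2.
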